Title:

Comparison of placement of double-lumen endobronchial tube using Glide Scope with 2 different stylet configurations vs standard Macintosh laryngoscopy.

Principal Investigator:[name], Emory University School of Medicine

V. 03April2015

NCT02495259

Title: Comparison of placement of double-lumen endobronchial tube using GlideScope with 2 different stylet configurations vs standard Macintosh laryngoscopy.

Principal Investigator: [name]
Emory University School of Medicine
Department of Anesthesiology

Site: Emory University Hospital (EUH) and Emory University Hospital – Midtown (EUHM)

IRB: Emory University School of Medicine

Purpose of Study

To evaluate the technique of placement of the double-lumen endobronchial tube (DLT) using an included stylet that has been radically bent (ZU-bend) as compared to a commercial GlideRite stylet with the GlideScope and direct laryngoscopy using Macintosh laryngoscope.

Introduction

Placement of the DLT is viewed as more challenging partly due to bulkiness and a lack of flexibility that the DLT has compared to single lumen endotracheal tubes, as well as a larger and more fragile occlusion balloon that is more prone to rupture. Securing an airway using traditional laryngoscopy as well as video-assisted indirect laryngoscopy each has its unique advantages and disadvantages.

In a recent study comparing laryngoscopy with Macintosh blade and GlideScope the former was concluded to be superior with respect to intubation success (1), while an earlier study indicated GlideScope to be equivalent to direct laryngoscopy (4). A follow-up editorial pointed out that in Russel's study there was no inclusion of the GlideRite stylet designed specifically for use with GlideScope and DLT, possibly explaining difficulties with GlideScope-assisted intubations (2, 3).

In a small anecdotal sample, the use of a radically curved DLT stylet, the ZU-bend, and GlideScope appeared to be useful in placement of the DLTs by multiple anesthetists under supervision of one anesthesiologist ([name], presented at Thoracic Anesthesia Symposium 2015).

Therefore, we propose to merge the study protocol similar to Russel et. al. (1) with inclusion of both the suggestions from Bussier's editorial , as well as the experience with radically bent DLT stylet (ZU-bend) to evaluate each method with respect to intubation ease and to compare the complication rate with each technique.

Investigational Devices

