The intubation modalities (GlideScope, Macintosh laryngoscope, GlideRite stylet and DLT intubating stylet) have all been approved for clinical use and have been used routinely at our institution for DLT placement.

Macintosh blade is one of the most commonly used direct laryngoscopy blades for both single and double-lumen endotracheal intubations. It allows the practitioner to visualize larynx for subsequent intubation.

The **GlideScope** is a video laryngoscope that provides a real-time view of the airway and tube-placement during intubation in place of the direct laryngoscope.

The **GlideRite Rigid stylet** is specifically designed to work with the GlideScope video laryngoscope to facilitate intubation. It provides necessary rigidity and curvature to an otherwise flexible endotracheal tube to permit easier manipulation of it for tracheal intubation.

ZU-bend is a specific shaping technique of the intubating stylet that is more closely related to GlideScope blade curvature. There is a commonplace practice of shaping a flexible stylet for intubation to suit a particular combination of patient and equipment variables. The degree of shaping is somewhat specific to each provider, and is a normal procedure for using the intubating stylet. Bending of the stylet prior to intubation constitutes a routine preparation step for the majority of intubations. The steps for shaping of the stylet are provided in the appendix A.

Objectives

The current research does not provide clear support for one method or another in DLT placement techniques. Additionally, our research has shown that the ZU-bend stylet may be useful with the GlideScope. This randomized controlled study will compare the efficacy of three different methods of DLT placement.

The primary outcome measures will be the mean time it takes to place a DLT with each modality. Secondary outcome measures include success rate of first endobronchial intubation attempt; assessment of difficulty by the provider and complication incidence.

The end points of evaluation of each technique were selected based on Russel's protocol with our modification as summarized in Table 1:

Table 1.

Metric:	Defined as:
First intubation attempt success	DLT placed during initial laryngoscopy, within 120s
Duration of laryngoscopy	Time from laryngoscope at pt's lips through 1 st EtCO ₂ detection
Blood on device	Yes/No
SpO ₂ <96% during intubation	Yes/no
Voice changes	Evaluated in PACU - subjective answer by patient

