Lip trauma	Evaluated immediately post-intubation
Dental trauma	--/--
Sore throat	Analog pain scale 0-10, subjective answer in PACU
DLT cuff rupture	Loss of air pressure during procedure requiring >1 reinflation
Ease of device placement	Multi-question form to be filled by anesthetist after intubation
Overall ease of intubation	Subjective score 0-10; where 0 – worst, 10-best
Laryngoscope insertion	--/--
Glottic view	--/--
DLT delivery	--/-- placement of DLT mouth → into glottis proximity
DLT placement	--/-- ease of placing DLT through glottic opening

Study design and methods

This is a prospective, randomized, three-armed trial to investigate the efficacy of a radically curved DLT stylet to facilitate GlideScope-assisted tracheal intubation (Group 1) as compared to the commercial standard of GlideScope with GlideRite stylet (Group 2) and a direct laryngoscopy with Macintosh blade and a regular DLT stylet (Group 3).

This study will not impart additional risks on the patient in excess of those routinely cited for placement of the double-lumen endobronchial tube. All of the modern intubation modalities will be available at the intubation time, arguably decreasing the risk of an ultimately failed securing of patient's airway.

Following informed consent, each subject will be identified via a unique alpha-numeric code and randomized to either of 3 initial DLT placement technique groups. In all cases, the other 2 intervention modalities will be available in the event of failed 1st attempt intubation and will be used at practitioner's discretion. Patient's medical history and detailed airway exam will be recorded on the study form, including Mallampatti score, thyromental distance, ability to prognathize the mandible, any limitation in neck flexion/extension, any evidence of poor dentition or pre-existing dental damage, patient's height, weight and BMI.

Patient will then be taken to the operating room and anesthesia will be induced in the standard fashion per provider's discretion after denitrogenation of patient with 100% O₂ until EtO₂ value is greater or equal to 80%.

Laryngoscopy with the specified randomization modality will be performed by the anesthetist or fellow with timing of intubation recorded as described above. DLT size used will be recorded on the form as well.

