The protocol in Russel's paper and previously cited data within their paper indicated that statistical significance can be attained at 30 subjects in each arm for 2 intervention comparison.

In our evaluation with 3 treatment arms, increasing sample size to 40 patients should provide adequate statistical power. Categorical data will be analyzed using Fisher's exact test. Mann-Whitney and Student's t-test will be applied where appropriate for continuous variables.

Adverse Event Reporting

The study team will comply with Emory University IRB policies for reporting adverse events. In this study, events that are determined by the Principal Investigator to be related to the research will be recorded and reported. Additionally, all deaths, related or unrelated, will be reported to the IRB. All events that are unanticipated problems that are related or possibly related to the research and place the subject or others at greater risk of harm than anticipated will be immediately reported to the Emory IRB.

Data and Safety Monitoring Plan

The data will be continuously analyzed to ensure there is not a significant trend that warrants early termination of the study. The PI will conduct monitoring after the first 10 patients are enrolled and again halfway through the study at 60 patients to evaluate for any related adverse events and ensure continued patient safety. Any serious complications encountered by the anesthesiologist in the room will be relayed to the principal investigator or co-investigators.

All investigators will complete the required training for conducting research at Emory University. All investigators will be made aware of the adverse event reporting policy and will report these events to the principal investigator in a timely manner.

References

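### Outside Table 1, recording of an adverse event rests on the Principal Investigator judging it related to the research; record first and judge relatedness separately

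*Combined protocol and SAP*

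**What the plan says.** **Recording rule (Adverse Event Reporting).** "events that are determined by the Principal Investigator to be related to the research will be recorded and reported". Two further routes lead to the IRB: "all deaths, related or unrelated, will be reported to the IRB", and "All events that are unanticipated problems that are related or possibly related to the research" that also put someone at greater risk than anticipated are reported immediately.

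**Monitoring (Data and Safety Monitoring Plan).** The Principal Investigator looks after the first 10 patients and again at 60 "to evaluate for any related adverse events and ensure continued patient safety". Separately, "Any serious complications encountered by the anesthesiologist in the room will be relayed to the principal investigator or co-investigators".

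**What the trial wants to know about harms.** The Introduction sets out "to compare the complication rate with each technique". The Objectives list, among the secondary outcomes, "assessment of difficulty by the provider and complication incidence". Table 1 then lists the evaluation end points: first-attempt success, blood on the device, SpO₂ below 96%, voice change, lip and dental trauma, sore throat and cuff rupture, together with timing and ease-of-use items. These carry a definition or a time of assessment (lip trauma, for example, is "Evaluated immediately post-intubation") and no relatedness condition.

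**The concern.** A relatedness test is an ordinary way to decide what goes to an IRB. Here the same sentence also decides what is recorded. An event that fails the test may leave no trace in the study data, and it may not be recoverable later.

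The test also asks about relatedness to the research, not to the intubation technique. The Investigational Devices section describes all the devices as approved and in routine local use, and Study design and methods says the study adds no risk beyond that of ordinary double-lumen tube placement. On that premise, an injury during placement can reasonably be classed as a routine risk of the procedure and therefore unrelated to the research. Yet harm from the technique is what the trial sets out to compare. Randomisation lets the arms be compared without case-by-case attribution, provided every event is recorded first.

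At stake are harms outside Table 1: whether the two safety looks can see them, and whether any tabulation of them by arm would be complete and even-handed.

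**Working it through.** **1. Which events meet the relatedness condition?** Setting the sections side by side:

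| Type of event | Route in the protocol | Relatedness test? | Expressly in study data by arm? |
|---|---|---|---|
| Table 1 harms and first-attempt success | Study end points | No | Yes, as end points of each technique |
| Deaths | IRB | No | Not stated |
| Unanticipated problems that raise risk | IRB, immediately | Related or possibly related; assessor not named | Not stated |
| Serious complications seen in the room | Relayed to the Principal Investigator or co-investigators | No | Not stated |
| Other events, e.g. malposition found at bronchoscopy, or laryngeal, tracheal or bronchial injury not handled as serious | Recorded and reported if the Principal Investigator finds them related | Yes | Only after passing the test |

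Study design and methods has tube position verified by bronchoscopy, auscultation and capnometry, but lists no result to be recorded. The gap is therefore the last row, plus uncertainty over whether the three rows above it reach the dataset.

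**2. Do the safety looks repair it?** No. They too are directed at related events.

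**3. Does it reach a planned outcome?** Complication incidence is not defined. If it means the Table 1 harms, the filter does not touch it. If it extends further, the filter does. No between-arm analysis of events outside Table 1 is specified.

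**4. How large could the effect be?** The protocol has no figure to reproduce: it gives no event rate and no attribution rate. What follows is illustration on assumed values. From the protocol: 40 evaluable patients per arm (Human Selection Criteria) and Fisher's exact test for categorical data (Statistical Analysis). Assumed: two-sided alpha of 0.05, true event rate r, and probability q that an event is judged related and so recorded. The recorded rate is r × q, and

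P(significant) = Σᵢ Σⱼ Bin(i; 40, r₁q₁) × Bin(j; 40, r₂q₂) × 1{Fisher p(i, j) ≤ 0.05}.

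*Equal true rates in two arms* (probability of a spurious significant difference; expected recorded counts 40 × r × q in brackets):

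| True rate | All recorded | q = 50% v 80% | q = 30% v 90% |
|---|---|---|---|
| 10% | 1.7% (4 v 4) | 1.8% (2 v 3.2) | 5.4% (1.2 v 3.6) |
| 20% | 2.8% (8 v 8) | 7.0% (4 v 6.4) | 25.9% (2.4 v 7.2) |
| 30% | 2.8% (12 v 12) | 11.8% (6 v 9.6) | 47.1% (3.6 v 10.8) |

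*Unequal true rates, 30% v 10%* (power):

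- All events recorded: 53%.
- Half judged related in both arms: 18%.
- Half judged related in the worse arm and all in the other: 5%.

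So the filter can create a difference or hide one, and it hides one even when applied equally to both arms.

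**5. What would an empty record mean?** With 0 recorded events in 40, the two-sided 95% exact upper limit is 1 − 0.025^(1/40) = 8.8%. That bounds the recorded rate. It bounds the true rate only if every event is recorded. If only half were recorded, the bound on the true rate would be 8.8% / 0.5 = 17.6%. Similarly, at the 60-patient look a true rate of 10% gives 60 × 0.10 = 6 expected events, of which 6 × 0.5 = 3 would be seen.

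**The case against.** The strongest reply is that this is an IRB-reporting sentence, and that the trial collects its harm outcomes elsewhere. Table 1 is presented as the list of end points, covers the common consequences of intubation, and has no relatedness condition. On that reading complication incidence is untouched. The text does not say that only related events are recorded, and deaths, certain unanticipated problems and serious complications have separate routes. What is left is mostly non-serious events outside Table 1, where the larger distortions in the illustration need rates of 20% to 30% that may be too high. At a true rate of 10%, with 25% v 75% judged related, 4 v 4 events become 1 v 3. The Fisher p-value for that table is 0.62, and the chance of a significant result is 3.1%, against 1.7% with full recording.

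Much of this stands and limits the point. It does not remove it. The sentence does say recorded, no other text provides for recording unlisted events regardless of relatedness, and the safety looks carry the same restriction.

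A reader might infer more than the documents support:

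- **That an unblinded Principal Investigator will favour one arm.** Blinding is not mentioned. The operator cannot be masked to the device, so lack of masking is a reasonable inference, but the exact statement is that no masking of the judgement is described. Nothing shows that it would be partial.
- **That the planned comparison of harms is filtered.** Table 1 items are not, and no comparison of other events is specified.
- **That failed intubation is lost.** First-attempt success is a Table 1 item for every patient.
- **That complication incidence is the basis of the safety looks.** Those looks are directed at related adverse events.

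**Conclusion.** The point holds within limits. For non-fatal events outside Table 1 that are not picked up as serious complications or unanticipated problems, recording depends on the Principal Investigator's opinion about relatedness to the research, with no criteria and no masking described. For events that do travel by those other routes, entry in the study data by arm is not stated. The consequence is for the safety looks after 10 and at 60 patients, and for complication incidence only if that term reaches beyond Table 1.

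The size is unknown because the documents give no event rate. The illustrative range, from almost no effect at a 10% true rate with moderately unequal attribution to a 47.1% chance of a spurious difference at 30% with extreme inequality, rests entirely on assumed rates, assumed attribution probabilities and an assumed two-sided alpha of 0.05. It shows that the effect can run in either direction; it does not estimate it. This is a cheap improvement to the completeness of harm data, not a demonstrated bias in a specified comparison.

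**What to change.** Replace the recording sentence in Adverse Event Reporting with wording such as: *All airway and respiratory adverse events not already listed in Table 1, from first laryngoscopy to the end of the PACU assessment, are recorded for every patient by assigned arm, whether or not they are thought related to the research. Relatedness is recorded as a separate field and governs reporting to the IRB only.*

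In the Data and Safety Monitoring Plan, have the looks after 10 and at 60 patients review all recorded events rather than related ones. It would also help to state in the Objectives whether complication incidence means the Table 1 harms alone, and, if feasible, to have relatedness judged by someone masked to arm.

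The cost is a few more lines on a form. The window is short, since follow-up already ends in the PACU; the recording change needs no extra staff, and IRB reporting obligations are unchanged. The downside is slightly more recording.

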Appendix A:

The stylet is then shaped as follows:

- The inside lumen of the tube and the stylet are lubricated with food-grade silicone spray such as SilkoSpray® by Rüsch.
- If the tube and stylet are separated for lubrication, they are reassembled for the subsequent steps.
- The tip of the endobronchial tube, approximately at the proximal end of the bronchial balloon is placed over the tip of the GlideScope blade with the bronchial lumen facing the lesser curvature of the GlideScope blade
- Proceeding from distal to proximal, the tube and the stylet are shaped to the outline of the GlideScope blade; the resulting curvature resembles "U" shape rather than a "J" of GlideRite. (Fig. 1, 2)
